Pain diary compliance will be reviewed by the study staff and reporting instructions will be reinforced. Adverse events will again be assessed by asking the subjects a nonleading question. Misuse and abuse-related events will be assessed using MADDERS (Analgesic Solutions, Wayland MA). Use of concomitant medications will be documented. Vital signs (blood pressure and pulse after sitting or lying supine for at least five minutes) will be measured. Blood (8 hour fast) and urine samples will be collected for chemistry, hematology, and urinalysis testing. Subjects will undergo a drug screen using a local urine testing kit. Female subjects will be tested for pregnancy using a local urine testing kit, if clinically indicated for females of childbearing potential. Female subjects of childbearing potential will be counseled to continue using highly effective contraception.

Subjects will be instructed to continue entering their average pain intensity and rescue medication use over the past 24 hours into their study-issued handheld device every night. Every morning upon awakening, subjects will complete the DSIS and confirm they have taken their study drug for the day via their study-issued handheld device, once completed. Subjects will be reminded on appropriate expectations around their participation in a clinical study and the importance of consistently and accurately reporting their pain throughout the study. Review of these educational materials will be repeated for all subjects at each site-based study visit via the aLearn® portal., with the exception of the final visit.

The following scales will be completed at Week 4 (Visit 4), Week 8 (Visit 5): FIQR, [REDACTED] PROMIS_{FM}, Patient Global Impression of Change (PGI-C) and S-STS.

Treatment Period: Week 12/Visit 6 or Early Termination Visit

During Week 12 (Visit 6) or the Early Termination Visit, subjects will return to the clinic for assessment of compliance with study drug and rescue medication use. The appropriate use of study drug and rescue medication will be assessed by inventory of the returned study drug and rescue medication, as well as by subject interview. Subjects will return the study-issued handheld device and any other study related materials to the study site.

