Pain diary compliance will be reviewed by the study staff. Adverse events will be assessed by asking the subjects a non-leading question. Misuse and abuse-related events will be assessed using MADDERS (Analgesic Solutions, Wayland, MA).

Use of concomitant medications will be documented. Vital signs (blood pressure and pulse after sitting or lying supine for at least five minutes) and body weight will be measured, a brief physical examination will be performed and subjects will undergo an electrocardiogram. Blood (8 hour fast) and urine samples will be collected for chemistry, hematology, and urinalysis testing. Female subjects of childbearing potential will be tested for pregnancy using a local urine testing kit. Subjects will undergo a drug screen using a local urine testing kit.

The site will contact the subjects by telephone within 7-10 days to complete a safety follow-up call. The Investigator, at their discretion, may ask subject to return for an Unscheduled Visit for any safety concerns, abnormal laboratory or ECG findings. A final call will be made to the subject approximately 30 days after the final visit to assess for AE closure and any new SAEs.

The following scales will be completed at Week 12 (Visit 6)/Early Termination Visit: FIQR, [REDACTED] PROMIS_{FM}, PGI-C, and S-STS.

Number of subjects (planned and analyzed):

Approximately 300 subjects will be randomized.

Inclusion Criteria: Screening

Subjects must meet ALL the following criteria to be enrolled in this study:

1. An Institutional Review Board approved written informed consent and privacy language (Health Insurance Portability and Accountability Act (HIPAA)) authorization must be obtained from the subject prior to performing any study-related procedures.
2. Subject provides separate consent to being included in a research subject database.
3. Subject is ≥ 18 and ≤ 75 years of age.
4. Subject must meet the following 3 conditions described in the 2016 American College of Rheumatology criteria for fibromyalgia [[Wolfe 2016](#)]:
 - a) Widespread Pain Index ≥ 7 and Symptom Severity Score ≥ 5 , or the Widespread Pain Index is 4 to 6 and the Symptom Severity Score is ≥ 9 .
 - b) Symptoms have been present at a similar level for ≥ 3 months; and
 - c) Pain is generalized and present in at least 4 of 5 regions.
5. Subject has a history of fibromyalgia that was diagnosed >1 year prior to Screening.

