6.2.11 Early Withdrawal Assessments

For the analysis, assessments performed at early withdrawal visits for the subjects who discontinued will be mapped to the closest visit, using midpoints between visits to window the early withdrawal. If the early withdrawal assessment is mapped to a visit where a scheduled assessment is already present, the scheduled assessment will take precedence, and the early withdrawal assessment will be disregarded (and listed only).

Note that the windowing will be specific to the measure, per the below table. For example, PGI-C is collected at Weeks 4, 8, and 12 and thus the early withdrawal assessment for PGI-C would be windowed with Day 2 to Day 42 as Week 4, Day 43 to Day 70 as Week 8, and Day 71+ as Week 12.

Assessment(s)	Timing of Early Withdrawal Assessment	Mapped Visit
Physical Exam	Day 2+	Week 12
Vital signs, Laboratory samples, PGI-C, FIQR, PROMIS _{FM} , PROMIS, ECG	Day 2 to Day 42	Week 4
	Day 43 to Day 70	Week 8
	Day 71+	Week 12
Sheehan STS	Day 2 to Day 21	Week 2
	Day 22 to Day 42	Week 4
	Day 43 to Day 70	Week 8
	Day 71+	Week 12

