6.12.3 Vital Signs

Descriptive statistics for observed values and changes from baseline in the following vital signs will be tabulated at each post-baseline visit:

- Systolic blood pressure (mmHg)
- Diastolic blood pressure (mmHg)
- Pulse rate (bpm)
- Body weight (kg)

All vital signs measurements throughout the study will be listed.

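### As written, early-termination body weights before Day 71 are windowed to Week 4 or Week 8, where the protocol text schedules no weight, instead of to Week 12 as for the physical examination

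*SAP*

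**What the plan says.** **SAP 6.2.11 (Early Withdrawal Assessments).** Early-withdrawal assessments "will be mapped to the closest visit, using midpoints between visits to window the early withdrawal". The section adds: "Note that the windowing will be specific to the measure, per the below table". The table has three groups.

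- Physical examination: Day 2 onward goes to Week 12.
- The group beginning "Vital signs, Laboratory samples, PGI-C, FIQR", which also holds the PROMIS scales and ECG: Day 2-42 to Week 4, Day 43-70 to Week 8, Day 71 onward to Week 12.
- S-STS: the same cut-offs plus a Week 2 window.

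A scheduled assessment in the same window takes precedence. SAP 6.2.12 treats unscheduled visits in the same way, at the lowest precedence.

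**SAP 6.12.3 (Vital Signs).** Observed values and changes from baseline "in the following vital signs will be tabulated at each post-baseline visit". The list is systolic pressure, diastolic pressure, pulse rate and body weight.

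**Protocol.** At Week 4 and Week 8 the Synopsis says "Vital signs (blood pressure and pulse after sitting or lying supine for at least five minutes) will be measured", with no weight; Section 10.3.2 agrees. At Week 12 or Early Termination it says "Vital signs (blood pressure and pulse after sitting or lying supine for at least five minutes) and body weight will be measured"; Section 10.3.3 lists body weight on its own line, apart from vital signs. Section 10.1 has weight at Visit 1 and Section 10.2 (Visit 2) has none. Section 9.3.2 limits vital signs to blood pressure and pulse, and Section 9.3.3 (Physical Examination) describes how weight is measured.

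**The concern.** The SAP moves weight into the vital signs for tabulation but gives it no window of its own. The vital-signs windows suit measures taken at Weeks 4, 8 and 12. Weight is taken after baseline only at Week 12 or early termination.

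For blood pressure and pulse, an early-termination reading joins, or gives way to, scheduled readings from the whole cohort. For weight there is nothing scheduled at Week 4 or Week 8 to join or give way to. A row with either label would describe dropouts and a few unscheduled weights, yet a reader would take it for the treatment group's mean at that visit. Week 12, the only scheduled post-baseline weight, would lack the final weights of everyone who left by Day 70. At stake is whether one descriptive safety summary can be read correctly.

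**Working it through.** **1. Reproduce the plan's cut-offs.** Visit days come from Protocol Table 3: Week 2 = Day 14, Week 4 = Day 28, Week 8 = Day 56, Week 12 = Day 84. A cut-off is the midpoint of neighbouring scheduled days.

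- Measures taken at Weeks 4, 8 and 12: (28 + 56)/2 = 42 and (56 + 84)/2 = 70. Both match the SAP table.
- S-STS, also taken at Week 2: (14 + 28)/2 = 21, then 42 and 70. All match.
- Physical examination, after baseline at Week 12 only: no neighbouring visit, so no cut-off, and Day 2 onward goes to Week 12. This matches.

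The rule in 6.2.11 therefore accounts for all three groups in its table.

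**2. Apply the same rule to body weight.** The only scheduled post-baseline day in the protocol text is Day 84. There is no midpoint, so every early-termination weight from Day 2 onward goes to Week 12, as for the physical examination.

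**3. Apply the SAP as written.** Under 6.12.3 weight is a vital sign, and under 6.2.11 vital signs use cut-offs 42 and 70. A weight taken at early termination on Day 30 becomes a Week 4 value; one taken on Day 60 becomes a Week 8 value. The precedence rule cannot displace either, because neither visit has a scheduled weight.

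**4. Size.** The documents give no dropout rate or timing. Assumptions: 100 treated per arm, 10% to 25% dropout, every dropout weighed at an early-termination visit, and the day of that visit uniform over Days 2-84 (83 days).

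| Window | Days | Share | 10 dropouts per arm | 25 dropouts per arm |
|---|---|---|---|---|
| Week 4 (Day 2-42) | 41 | 41/83 = 49% | 4.9 | 12.3 |
| Week 8 (Day 43-70) | 28 | 28/83 = 34% | 3.4 | 8.4 |
| Week 12 (Day 71-84) | 14 | 14/83 = 17% | 1.7 | 4.2 |

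Outside Week 12: (41 + 28)/83 = 69/83 = 83%. That is 10 × 0.83 = 8.3 to 25 × 0.83 = 20.8, or roughly 8 to 21 weights per arm. The figure falls in proportion if some dropouts do not attend the visit.

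**5. Was it corrected later?** The post-database-lock addendum changes the prior-medication definition and several efficacy sections. It does not touch 6.2.11 or 6.12.3.

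**The case against.** The strongest reply is that the SAP never says this outright. The window table does not name body weight. The protocol keeps weight apart from vital signs and describes its measurement under the physical examination. A programmer who gave the table's labels their protocol meaning, or who relied on the measure-specific note, would send weight to Week 12 from Day 2. That stands as a limit on how firmly the point can be put: it is a conflict that arises through 6.12.3, not an explicit instruction. It does not remove the need for a stated rule, since 6.12.3 is the only place where the SAP plans a post-baseline weight summary and it calls weight a vital sign. SAP 6.3.3 relies on independent programming, and two programmers could reasonably differ.

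It also stands that the table shells are a separate document (SAP 6.3.6), so we cannot see whether Table 14.3.6.1 has Week 4 and Week 8 weight rows. Every post-baseline visit could mean every visit at which the variable is collected.

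A reader might infer more: that the Week 12 weight change becomes a completer analysis, biased by selection on outcome. The documents do not support that. Early-termination weights from Day 71 do reach Week 12. Earlier ones are displaced, not lost, and SAP 6.12.3 lists all vital-sign measurements. The Week 12 rows for blood pressure, pulse, laboratory values and ECG leave out the early-termination readings of the same subjects; weight differs only in having no earlier scheduled row.

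Finally, calling a Day 5 weight a Week 12 value mixes a few days of exposure with twelve weeks and could dilute a change that builds over time. That is a fair criticism of a plain relabelling, and the fix has to deal with it.

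In the extracted text of Protocol Table 3, the body-weight row is marked only at Visit 1. The table may be broken, and the Synopsis and Section 10.3.3 clearly place weight at Week 12/Early Termination.

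**Conclusion.** The point holds as a minor inconsistency. Read together as written, SAP 6.2.11 and 6.12.3 send early-termination weights from Days 2-70 to visits with no scheduled weight, against the section's own closest-visit rule. Any Week 4 and Week 8 weight summaries would then consist of early terminators and unscheduled weights, and the Week 12 change would omit subjects who left by Day 70.

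The size, roughly 8 to 21 weights per arm, rests entirely on the assumptions in step 4 of the working. A reader might take the whole 10 to 25 dropouts per arm as affected. That would need every one of them to leave by Day 70 and be weighed, which the documents do not say.

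Protocol 12.7 makes all safety summaries descriptive, and neither document names weight as a safety endpoint. No efficacy result, hypothesis test or stopping criterion is affected. The change is worth making because it is nearly free and removes rows that would mislead; nothing in the trial's conclusions depends on it.

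**What to change.** - In SAP 6.2.11, give body weight its own line: Day 2 onward, mapped to a row labelled as Week 12 / last on-study weight.
- In SAP 6.12.3 and the shell for Table 14.3.6.1, do not summarise body weight at Week 4 or Week 8. Any unscheduled weights stay in the listing.
- Leave blood pressure and pulse as they are.

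The cost is one line in the window table and one shell. If the outputs already exist, a documented correction or a footnote in the study report is enough. The downside is that the combined row mixes exposure durations. The label makes that visible, and a line restricted to scheduled Week 12 weights can be shown beside it.

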6.2.12 Unscheduled Visits

Unscheduled visits will be handled in an identical manner to early withdrawal assessments. If this results in multiple records for a given visit, then the scheduled visit will take highest precedence, followed by early withdrawal visits, and unscheduled visits last.

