- p Urine drug screen kit for local testing.
- q Includes prior medications taken within the last 30 days.
- r Adverse events will be collected from the time of study drug administration through the last day of the subject's participation in the study. Serious adverse event reporting will begin at the time informed consent is obtained and will end 30 days after last dose of study drug.
- s To be completed by Investigators or qualified Subinvestigators when potential abuse-related events are identified and upon the completion of each subject's participation in the study.
- t Subjects will complete the PROMIS_{FM} sleep disturbance, fatigue profile and physical function short form questionnaires.
- u Screening ECGs will be collected in triplicate (at least two (2) minutes apart). All other ECGs will be single ECGs.
- v Visit Three (3) will be completed by telephone or videoconference. The subject will be asked to complete the printed copy of the S-STS given to them at their Baseline Visit while communicating with the site staff. The staff will review the subject's answers to the S-STS and recommend corrections, only where the form has been completed incorrectly. The completed S-STS source document will be mailed back to the clinic or returned at the next study visit to be filed in the subject's chart and entered into the eCRF system.
- w To be measured without shoes.
- x To be obtained with a calibrated scale and subject must remove shoes and bulky layers of clothes.
- y A safety follow-up call should be completed 7-10 days after Visit 6 completion. Final safety follow-up call to be made 30 (±5 days) days after Visit 6 completion. Investigator may ask subject to return for Unscheduled Visit, as needed.

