6.2.3 Duration / Study Day / Time

Study day will be calculated as the number of days from first dose of study drug.

- date of event – date of first dose of study drug + 1, for events on or after first dose
- date of event – date of first dose of study drug, for events before first dose

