6.12.2 Laboratory Data

Descriptive statistics for the observed values and change from baseline will be presented by treatment group and visit for each hematology, urinalysis, and serum chemistry (including triglycerides and thyroid panel) parameter. Each continuous measurement will be classified as below, within, or above normal range, based on ranges supplied by the laboratory used. Categorical parameters may also be classified as normal or abnormal based on normal ranges, and subject counts within each category will be summarized. Shift tables in relation to the normal range from baseline to each post-baseline visit will be presented.

Summaries and listings will be presented using the original unit for each parameter as received from the analytical laboratory.

A listing of out of normal range laboratory values throughout the study will be presented. All laboratory assessments, including urine pregnancy tests, drug tests, and serology will also be listed.

A separate listing will be provided for all Alanine Aminotransferase (ALT), Aspartate Aminotransferase (AST), and Bilirubin results at all timepoints for any subjects who meet the criteria for liver function abnormalities as defined in Section 0.

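### Unscheduled visits are assigned to study weeks by study day alone, so off-drug rechecks after early termination can be tabulated as Week 8 or Week 12 safety results

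*SAP*

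**What the plan says.** **Windowing.** SAP 6.2.11 sets the rule for early withdrawal assessments, which "will be mapped to the closest visit, using midpoints between visits to window the early withdrawal". Its worked example for PGI-C is "windowed with Day 2 to Day 42 as Week 4, Day 43 to Day 70 as Week 8, and Day 71+ as Week 12", and its table applies the same three windows to vital signs, laboratory samples, ECG, FIQR and PROMIS. SAP 6.2.12 extends the rule: "Unscheduled visits will be handled in an identical manner to early withdrawal assessments".

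**Time origin.** SAP 6.2.3: "Study day will be calculated as the number of days from first dose of study drug".

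**Competing records.** If several records fall in one window, SAP 6.2.12 says "then the scheduled visit will take highest precedence, followed by early withdrawal visits, and unscheduled visits last".

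**Recall after treatment.** Protocol 6.1 and 10.3.3 let the investigator bring a subject back after the final visit because of a safety concern or an abnormal laboratory or ECG result. Table 3, footnote y, puts a first follow-up call 7 to 10 days after Visit 6 and a final call at 30 ± 5 days, then adds: "Investigator may ask subject to return for Unscheduled Visit, as needed".

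**Use of the windowed values.** For laboratory data, SAP 6.12.2 says: "Shift tables in relation to the normal range from baseline to each post-baseline visit will be presented". SAP 6.12.3 and 6.12.4 tabulate vital signs and ECG by visit, and 6.12.4 adds ECG shift tables. None of these sections, nor the post-lock addendum, limits the windows by last dose or end of treatment.

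**The concern.** A subject who stops early attends an Early Termination visit and then has no further scheduled records. The windows after that visit are empty, so the precedence rule has nothing to rank above an unscheduled record there. A recheck made off drug becomes that subject's Week 8 or Week 12 value in the assigned arm's column. Table 3 of the protocol places those weeks in the Treatment Period, and a reader of the tables would naturally take the values as belonging to it.

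Two things are at stake. The late by-visit summaries mix on-drug and off-drug measurements without marking which is which. The added values are also a selected set, because subjects are recalled for safety concerns or abnormal findings while other early terminators contribute nothing to those weeks.

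**Working it through.** **Step 1: reproduce the window limits.** Table 3 gives the nominal days: Week 2 = 14, Week 4 = 28, Week 8 = 56, Week 12 = 84. The midpoints are (14 + 28)/2 = 21, (28 + 56)/2 = 42 and (56 + 84)/2 = 70. All three match SAP 6.2.11; Day 21 is used only for the S-STS. The final window has no upper limit.

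**Step 2: state when a recheck is counted.** Let *d* be the day of Early Termination and *L* the lag to the recheck. The recheck is dated *d* + *L*. If it falls in the same window as the Early Termination record, that record or a scheduled one outranks it. If it falls in a later window, no scheduled or early withdrawal record exists there and the recheck is used.

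**Step 3: count.** Take *d* = 2 to 79, which is 78 days; Day 80 opens the Week 12 visit window (84 ± 4). The lags are assumptions borrowed from the two follow-up calls, with the recheck made on the day of the call.

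| Lag *L* | Termination days moved to a later window | Count | Share of 78 days |
|---|---|---|---|
| 7 | 36–42, 64–70 | 7 + 7 = 14 | 18% |
| 10 | 33–42, 61–70 | 10 + 10 = 20 | 26% |
| 25 | 18–42, 46–70 | 25 + 25 = 50 | 64% |
| 30 | 13–70 | 28 + 28 + 2 = 58 | 74% |
| 35 | 8–70 | 28 + 28 + 7 = 63 | 81% |

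In the last two rows the terms are moves from Week 4 to Week 8, from Week 8 to Week 12, and from Week 4 straight to Week 12.

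**Step 4: single cases.**
- Termination on Day 40, recheck 7 days later: Day 47, tabulated as Week 8.
- Termination on Day 50, recheck 30 days later: Day 80, tabulated as Week 12.
- Termination on Day 30, recheck 10 days later: Day 40, still Week 4, so the recheck is outranked and not tabulated.
- Termination after Day 70, or a completer: the recheck stays in the Day 71 onward window and is outranked, unless that parameter is missing at the final visit.

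**Step 5: direction.** Let *n* other subjects in the arm have mean *m* at that week, and let the recheck be *x*. Including it changes the mean by (*x* − *m*)/(*n* + 1). A recheck that is still raised moves the mean up, and one below *m* moves it down. With 100 subjects planned per arm (SAP Section 4), one value carries a weight of 1/100 = 1% if everyone contributes, and more as dropouts reduce *n*.

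**The case against.** The strongest reply is that this is a convention in descriptive tables whose effect is probably small. Protocol 12.7 plans no safety testing. SAP 6.12.2 to 6.12.4 speak of post-baseline visits and never call the values on-treatment, and the TEAE definition in SAP 6.12.1 also runs to the end of participation. Individual data stay visible: out-of-range laboratory results, vital signs and ECGs are listed, and subjects meeting the liver criteria of SAP 6.2.25 have all their ALT, AST and bilirubin results listed. All of this stands and limits the weight of the point. It does not correct the visit label in the summaries and shift tables.

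A reader might go further and infer that the rule pulls the late summaries towards normal in an arm with more toxicity. The documents do not support that. A subject who has stopped has no on-drug Week 8 or Week 12 value to compare with; the alternative is no value, and removing a recheck that is still raised would make the table look better. The pattern of enzymes rising on drug and falling afterwards (Protocol Section 4) comes from one subject in a 200 mg period, whose GGT was still above range at last evaluation. This trial uses 50 and 100 mg. Protocol 6.3 reports no difference from placebo in the earlier adverse event profile, so more recalls in an active arm cannot be presumed.

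The 30-day count is also less secure than the 7- and 10-day counts. The text of Protocol 6.1 and 10.3.3 attaches the optional return visit to the first call and describes the final call as a check on AE closure and new SAEs. Only footnote y mentions the return visit after both calls.

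**Conclusion.** The gap is real and minor. Followed as written, the SAP lets off-drug rechecks of subjects who terminated early enter the Week 8 or Week 12 laboratory, vital-sign and ECG summaries and the laboratory and ECG shift tables. The direction of the resulting distortion cannot be determined from the documents.

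The reach of the rule is 14, 20 or 58 of 78 termination days for rechecks 7, 10 or 30 days later. It would be wrong to read 58 of 78 as about three quarters of early terminators. The shares treat every termination day alike and assume a recheck at a fixed lag. How many subjects terminate early and are then recalled is not given, and it may be few.

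Completers are largely protected by their scheduled Week 12 record. PGI-C, FIQR, PROMIS and S-STS are exposed only if completed at an unscheduled visit. A reader might also fear for the primary analysis, but NRS weeks come from the diary under SAP 6.2.17.2, not from these visit windows.

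**What to change.** Add to SAP 6.2.11–6.2.12: unscheduled assessments dated after the subject's Visit 6/Early Termination visit, or more than a pre-stated short lag after last dose, are not windowed to a treatment visit; they are summarised under a separate post-treatment follow-up label and listed. Both dates are needed, because a cut at the Early Termination visit alone would still admit off-drug values taken between last dose and that visit. The sponsor should state the lag; the documents give none.

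The same edit could say which record is used when two unscheduled records fall in one window, which 6.2.12 leaves open.

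The cost is one sentence, a date check in programming and slightly fewer observations in the late by-visit summaries. The addendum shows that the SAP was already being amended after database lock and unblinding. If the change is made at that stage, it should be declared as such, and the affected tables can be added with a documented reason, as SAP Section 6 allows.
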